7.2 SERIOUS ADVERSE EVENT

A **serious** adverse event (SAE) is any adverse event occurring at any dose that suggest a significant hazard or side effect, regardless of the Investigator or Sponsor's opinion on the relationship to the investigational product and that results in, but may not be limited to, any of the following outcomes:

- death (regardless of the cause)
- a life-threatening adverse drug experience
- inpatient hospitalization or prolongation of existing hospitalization (any inpatient hospital admission that includes a minimum of an overnight stay in a health care facility)
- a persistent or significant disability/incapacity

a congenital anomaly or birth defect.

Important medical events that may not result in death, be life-threatening or require hospitalization may be **serious** when, based upon appropriate medical judgment, they may jeopardize the subject and may require medical or surgical intervention to prevent one of the outcomes listed above.

Hospitalization for elective treatment of a pre-study condition that did not worsen while on study and hospitalizations for treatment of non-adverse events (e.g., cosmetic surgery) are not considered serious adverse events.

Significant medical events are those, which may not be immediately life-threatening, but may jeopardize the subject and may require intervention to prevent one of the other serious outcomes listed above. Examples of such events are intensive treatment in an emergency room or at home for allergic bronchospasm; blood dyscrasias or convulsions that do not result in hospitalization; resulting in an adverse event will normally be considered serious by this criterion.

Inpatient hospitalization or prolongation of existing hospitalization means that hospital inpatient admission and/or prolongation of hospital stay were required for treatment of AE, or that they occurred as a consequence of the event. Hospitalization for elective treatment of a pre-study condition that did not worsen while on study and hospitalizations for treatment of non-adverse events (e.g., cosmetic surgery or diagnostic procedure) are not considered serious adverse events.

Any new SAE that occurs after the study period and is considered to be related (possibly/probably) to the investigational product or study participation should be recorded and reported immediately.

A **life-threatening** adverse drug experience is any adverse event that places the subject, in the view of the Investigator, at immediate risk of death from the reaction as it occurred, i.e., it does not include a reaction that, had it occurred in a more severe form, might have caused death

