8.3.7.1 Adverse Events

Adverse events will be coded to system organ class and preferred term using the latest version of Medical Dictionary for Regulatory Activities (MedDRA) and are graded by the Investigator in terms of severity and relation to study treatment. All data will be listed by subject. Only treatment emergent AEs (TEAEs) will be presented in summary tables.

TEAEs are the adverse events that occur during the observation period, and the pre-treatment adverse events or pre-existing medical conditions that worsen in intensity after start of study medication and within the observation period.

TEAEs will be summarized by treatment arm in terms of crude incidence rates. For each event the crude incidence rate is defined as the number of subjects experiencing the event divided by the number of subjects initially exposed to study drug, regardless of duration of exposure to study drug. In addition, for each event the worst severity grade and the "worst" Investigator's judgment on study drug relationship is considered for each subject and frequency tables by worst severity grade and by worst study drug relation are provided. In this analysis, a subject having experienced more than once events classified under the same preferred term (body system) will be counted only once in the number of subjects with that preferred term (body system).

Summaries of TEAEs will be presented by body system and by preferred term within each body system (MedDRATM Terminology). The percentage of subjects who experienced AEs coded with the same term will be tabulated by treatment group in descending order according to the incidence of AEs in the active treatment groups.

All reported adverse events will be listed independently of their onset date. Serious Adverse Events, causes of death and AEs leading to premature discontinuation of study drug will be summarized similarly and listed. Reasons for premature discontinuation of study drug will be listed and summarized by frequency tables on all analysis sets.

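### Protocol 7.2 makes a judgement of hazard or side effect a condition of seriousness, so a listed outcome such as an overnight hospital admission is not by itself enough to make an event an SAE

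*Protocol*

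**What the plan says.** The defining sentence in Protocol 7.2 has three parts.

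- The event must be "any adverse event occurring at any dose that suggest a significant hazard or side effect".
- This applies "regardless of the Investigator or Sponsor's opinion on the relationship to the investigational product".
- The sentence then continues "and that results in, but may not be limited to, any of the following outcomes". The list is death from any cause, a life-threatening experience, inpatient hospitalisation or its prolongation, persistent or significant disability, and congenital anomaly.

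The hospitalisation item carries its own gloss: "any inpatient hospital admission that includes a minimum of an overnight stay in a health care facility". The section names the admissions that do not count. The first is "Hospitalization for elective treatment of a pre-study condition that did not worsen while on study"; the other is admission for something that is not an adverse event. A separate paragraph allows important medical events outside the list to be treated as serious on medical judgement.

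Two things depend on the definition. Protocol 4.5.2 and 7.4 require SAEs to reach the sponsor within 24 hours. Protocol 8.3.7.1 states that "Serious Adverse Events, causes of death and AEs leading to premature discontinuation of study drug will be summarized similarly and listed", and SAP 9.3 repeats the AE outputs for the serious subset. Protocol 2.1 makes safety part of the primary objective.

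**The concern.** Seriousness is normally settled by outcome, so that two sites seeing the same admission classify it alike and causality is assessed separately. Here a further test stands in front of the outcome list. The protocol gives no criterion for a significant hazard and does not say who decides. The other half of the test, side effect, is by ordinary meaning a judgement about the product, which the next clause of the same sentence says should play no part.

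At stake is whether an in-study event with a listed outcome is sent to the sponsor within 24 hours and counted in the SAE tables. Protocol 1.2.2 records no earlier study of bertilimumab in ulcerative colitis and 45 people exposed intravenously. Protocol 1.3.1 describes the earlier trials as single-dose. Protocol 1.3.2 reports three infusion reactions, one of them serious. With so little prior experience of repeated dosing, the classification should not turn on an undefined judgement that may vary between sites.

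**Working it through.** The plan gives no figure to reproduce. The check is a reading of the definition against the text around it.

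**1. Logical form.** As written:

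SAE = adverse event AND (suggests a significant hazard OR is suggestive of a side effect) AND (listed outcome).

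An event falls outside if it is judged to be neither a significant hazard nor a side effect, even when the outcome is on the list.

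**2. Does other wording remove the middle term?**

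| Text | What it does | Removes the hazard test? |
|---|---|---|
| 7.2, opinion on relationship set aside | Excludes causality opinion only | No, opinion on hazard remains |
| 7.2, outcome list said not to be exhaustive | Widens the outcome side | No |
| 7.2, important medical events | Adds a second route for events that may not meet the list; permissive and also based on judgement | No |
| 7.2, hospitalisation gloss and exclusions | Point to seriousness by outcome | Not expressly; they conflict with it |
| 7.2, death counted whatever the cause | Points to seriousness by outcome | Not expressly; it conflicts with it |
| SAP 9.3 | Restricts the AE outputs to SAEs, with no definition of seriousness | No |

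No sentence in either document says that a listed outcome is sufficient alone.

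**3. Intent.** Where 7.2 wants a relatedness filter, for new SAEs arising after the study period, it states one openly. That and the narrow exclusions suggest the in-study filter is a drafting accident. Even so, an investigator is left with two readings and no rule for choosing between them.

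**4. Which outcomes are exposed in practice?** A life-threatening event is defined as one placing the subject "at immediate risk of death from the reaction as it occurred", which cannot sensibly be called no significant hazard. Death is listed whatever its cause. The working gap is hospitalisation and, less often, disability. Take an overnight admission for an infection that the investigator regards as unremarkable and unconnected with treatment. Under the literal sentence it fails the middle term. Under the gloss and exclusions in the same section it is an SAE.

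**5. What is lost.** Protocol 5.6.1 records every AE. Protocol 8.3.7.1 and SAP 9.3 list them all by subject, and the SAP listing shows whether each was serious. The event therefore stays in the data. Its SAE status, the 24-hour notification and its place in the SAE summaries are what could go.

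**6. Scale of one event.** Assume the maximum of 42 subjects, split exactly 2:1 and all treated: 42 × 2/3 = 28 active and 42 × 1/3 = 14 placebo. One reclassified subject then moves that arm's SAE incidence by 1/28 = 3.6 percentage points or 1/14 = 7.1 percentage points. This is the granularity of the table, true of any single miscount. It says nothing about how often the phrase would cause one.

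**The case against.** The best defence is that the section, read as a whole, already defines seriousness by outcome. It covers any overnight admission, states twice which hospitalisations do not count, counts death from any cause and sets aside opinion on relationship. An admission judged not hazardous is not among the exclusions. Many sites would probably report it anyway. This is a good argument about intent and lowers the likely frequency of error. It does not remove the conflict, because the governing sentence still joins the two conditions and nothing gives the specific text priority over it.

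Several stronger readings might be inferred, and the documents do not support them.

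- *That life-threatening events escape.* The definition in 7.2 rules this out in any practical sense. Protocol 9.1 also names life-threatening conditions and death separately from SAEs in the reports to the ethics board.
- *That events go unrecorded.* They remain AEs and are listed.
- *That colitis flares are the main casualty.* Whether a flare is an AE at all depends first on the sentence about disease-related events in Protocol 7.1. That sentence is itself unclear and is a separate problem.
- *That omissions could reverse the comparison between arms.* The documents give no expected SAE rate, the safety analysis is descriptive, the trial is double-blind, and nothing in the wording would act on one arm more than the other.

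**Conclusion.** The point holds as an internal contradiction in Protocol 7.2. Taken literally, the sentence lets an overnight admission or a disability fall outside the SAE definition on an undefined judgement, and neither document overrides it. The consequence is limited to the SAE label, the 24-hour report and the SAE summaries.

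The size cannot be computed, because it depends on how sites apply the sentence; it is probably small. The conclusion rests on the ordinary meaning of and in the definition, and on the absence of an overriding definition in the protocol or SAP. It does not rest on any assumed SAE rate. The wording should be corrected because it governs safety capture in a study whose primary objective includes safety, and because the correction costs almost nothing.

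**What to change.** In the first sentence of Protocol 7.2, delete the phrase requiring the event to suggest a significant hazard or side effect, and the and before the outcome clause that would be left stranded. An SAE is then any adverse event at any dose, "regardless of the Investigator or Sponsor's opinion on the relationship to the investigational product", that results in one of the listed outcomes. A listed outcome is then sufficient alone. The important-medical-event paragraph and the stated hospitalisation exclusions can stay as they are.

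Before database lock, check AEs that have a recorded hospital admission but are marked non-serious against the revised sentence, and query any that meet it.

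This edit does not settle the disease-related sentence in Protocol 7.1, which needs its own clarification.

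The cost is a change to one sentence, a notice to sites and a targeted check. A few more SAE reports may follow. No endpoint or planned analysis changes.

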7.3 DEFINITION OF AN UNEXPECTED ADVERSE EVENT

An **unexpected** adverse drug experience (event) is any adverse event, the specificity or severity of which is not reported in the current Investigator's brochure.

7.4 NOTIFICATION ABOUT SERIOUS OR UNEXPECTED ADVERSE EVENTS

All SAEs must be reported **immediately** to the Immune Pharmaceuticals representative as soon as it becomes known to the Investigator and not later than within 24 hours of their knowledge of the occurrence of an SAE. The notification will occur via data entry to the EDC with phone/fax/text/email notification to the Sponsor. Immune Pharmaceuticals Representative:

These preliminary reports will be followed within 24 hours by detailed descriptions that will include a completed SAE form, copies of hospital case reports, autopsy reports and other documents, when requested and applicable.

In addition, all AEs / SAEs / Suspected Unexpected Serious Adverse Reaction (SUSARs) will be reported to the local EC and regulatory authorities as required by local regulations and ICH-GCP guidelines.

Minimal information should include:

- An identifiable subject (e.g., Subject randomization number)
- An identifiable reporting source
- All related adverse events
- The suspect medicinal product
- Follow-up of SAEs / SUSARs
- Follow-up of SAEs / SUSARs that occur during the study will continue until their satisfactory resolution or stabilization.

If, when supplementary information is available, a follow-up SAE Report Form must be completed by the site and data entry inputted to the EDC with follow-up phone/fax/text/email to Sponsor within 24 hours.

The contact information for follow up SAE reporting is the same as for initial SAE reports (see above section).

The paper copy of the SAE form and accompanying documentation should be placed in the SAE section of the Investigator's file. If supplementary information on a SAE has to be sent, the SAE form has to be used marked as "follow-up report."

Follow-Up Reports on non-serious AEs

All AEs must be followed until resolution or stabilization. In outstanding cases, it may be defined as "ongoing without further follow-up" by the Investigator and Sponsor's decision.

8. PLANNED STATISTICAL ANALYSES AND METHODS

A statistical analysis plan (SAP) will be written and finalized before the study closure, i.e., database closure and unblinding of the randomization code. The SAP will provide full details of the analyses, the data displays and the algorithms to be used for data derivations. The SAP will include the definition of major and minor protocol deviations and the link of major protocol deviations to the analysis sets.

8.2 DETERMINATION OF SAMPLE SIZE

This is the first study investigating clinical outcome of treatment with bertilimumab in UC patients, and is therefore exploratory. Consequently, this trial's analyses are descriptive in nature and whose sample size has been chosen, in consultation with physicians in the field and based on studies with similar objectives in the literature^m, to provide reasonable precision

Protocol: Immune/BRT/UC-01 Page 38 of 58 Final Version 8.0 May 23, 2018

^m Parikh, A. et al. Vedolizumab for the treatment of ulcerative colitis: a randomized controlled phase II doseranging study. Inflammatory Bowel Disease, 2012; *18*:1470-1479.

in initial estimation of the drug's clinical effect at one dose level. Specifically, up to 42 subjects will participate in this trial.

8.3 STATISTICAL METHODS

All measured variables and derived parameters will be listed individually. Outcomes will be summarized by treatment group, depending on their nature, as follows:

- For dichotomous variables: Categorization into success/failure-like categories; then incidence of failure and relative risk of failure in the active group compared to placebo with 95% confidence interval.
- For numeric continuous endpoints: Descriptive statistics and summary tables will include sample size, arithmetic mean, standard deviation, median, minimum and maximum, and 95% Confidence Interval (CI) for mean at the relevant time points by treatment.
- For ordered categories endpoints: incidences in the different categories and, after dichotomization into success/failure-like categories, incidence of failure and relative risk of failure by treatment with 95% confidence intervals.

All tests applied will be two-tailed, and p value of 0.1 or less will be considered statistically significant. Since this is an exploratory trial, there will be no Alpha-correction for multiple testing. The data will be analyzed using the SAS® 9.1 software package or higher (SAS Institute, Cary, North Carolina).

8.3.1 Analysis Sets

8.3.1.1 Safety Analysis Set

The Safety Analysis Set will include all subjects who were exposed to any of the study treatments.

8.3.1.2 Modified Intent to Treat Analysis Set

The modified intent to treat (mITT) analysis set will include all randomized subjects who received at least one dose of study treatment (placebo or bertilimumab), and had at least a full Mayo score at screening and at least one post-baseline partial Mayo score from visit 3 onward. Excluded from mITT will be subjects with major entry violations as determined by blind review.

Missing primary efficacy data in mITT will be imputed as follows:

Full Mayo Score at Visit 7:

- Subjects with a Full Mayo Score post-screening prior to Visit 7 (and none at Visit 7) will have their Visit 7 score imputed by last observation carried forward (LOCF).
- Subjects with a Full Mayo Score after Visit 7 (and none at Visit 7) will have their Visit 7 score imputed by last observation carried backward (LOCB).
- Subjects with only partial Mayo score(s) from Visit 3 onward will have their Full Mayo Score at Visit 7 imputed by multiple imputation (MI), using a model that includes screening data, treatment and partial Mayo Score.ⁿ

UCEIS (a secondary endpoint that will be analyzed in mITT as well)

Protocol: Immune/BRT/UC-01 Page 39 of 58 Final Version 8.0 May 23, 2018

ⁿ a) The continuous Full Mayo Score will be imputed using MI, after which clinical response will be computed and b) Should there be variables causing the MI model not to converge, these will be excluded from the model.

- Subjects with UCEIS post-screening prior to Visit 7 (and none at Visit 7) will have their Visit 7 score imputed by last observation carried forward (LOCF).
- Subjects with UCEIS after Visit 7 (and none at Visit 7) will have their Visit 7 score imputed by last observation carried backward (LOCB).
- Subjects with no post-screening endoscopy will have their UCEIS at Visit 7 imputed by MI using screening data, treatment and partial Mayo Score (from Visit 3 onward).^o

8.3.1.3 Per Protocol Analysis Set

The per protocol (PP) analysis set will be a subset of mITT subjects who had no major protocol violations likely to affect outcome as determined by blind review and who received at least 2 of 3 study treatments (placebo or bertilimumab) and who had a full Mayo score at screening and at visit 7. Only observed data will be used in PP; primary data will not be imputed.

8.3.2 Subject Disposition

Major and minor protocol deviations will be identified by medically trained staff before the study closure. All screened subjects will be accounted for; enrolled subjects will be followed to completion. Protocol violations determining the belonging of subjects to the different analysis sets will be summarized. A full disposition tree will be generated displaying the number of subjects reaching the different phases of the study (screening, randomization/treatment, end of treatment, end of study) and the main reasons for exclusion.

8.3.3 Demographics and Baseline Characteristics

Baseline demographics and disease characteristics will be summarized for the safety analysis. Continuous demographic variables and baseline/screening disease characteristics will be summarized by mean, median, standard deviation, minimum and maximum. Qualitative demographic characteristics and baseline/screening disease characteristics will be summarized by counts and percentages. Other subject characteristics (medical history, clinical findings, inclusion/exclusion checklist, etc.) will be listed only.

These variables will be compared between the treatment groups in a descriptive fashion; no formal statistical testing will be performed.

Previous and concomitant medications will be coded according to the WHO drug code and the ATC class code. They will be summarized by type (e.g., previous, concomitant, for AE) by tabulating the number and percentages of subjects having received each treatment.

8.3.4 Efficacy Endpoints Analysis

Analysis of all efficacy endpoints will be performed on the mITT set. The PP set will be used as supplementary analyses to test the robustness of the results. If deemed appropriate, supportive analyses using multiple imputations for missing data will be performed on the primary and secondary endpoints. Additional exploratory data-driven analyses could be performed with the caveat that any statistical inference will not have any confirmatory value. Because this is an exploratory study, alpha will be set at 0.1 for comparisons between groups.

8.3.4.1 Primary Endpoint Analysis

This study's primary endpoint analyses will be descriptive, providing proportion of Mayo Score Clinical Response separately by treatment group, including two-sided 95% Exact

Protocol: Immune/BRT/UC-01 Page 40 of 58 Final Version 8.0 May 23, 2018

^o a) The continuous UCEIS will be imputed using MI, after which clinical response will be computed and b) Should there be variables causing the MI model not to converge, these will be excluded from the model.

Binomial confidence intervals. Exploratory statistical testing will be done by comparing Bertilimumab treatment arm to placebo.

8.3.4.2 Secondary Endpoint Analyses

- a. Primary endpoint analysis described in the preceding section will be repeated in PP.
- b. Secondary endpoints will be analysed in both mITT and PP analysis sets.

8.3.5 Pharmacokinetic Analysis

To the degree possible given the limited number of sampling timepoints, PK parameters will include AUC, T_{max} , C_{max} , C_{avg} , C_{min} , and $t_{1/2}$. The PK parameters will be summarized by descriptive statistics (i.e., mean, standard deviation, standard error, geometric mean, median, minimum and maximum) by treatment group and by timepoint. Additional analyses may be performed if deemed necessary.

